# 7.2 Planned Analyses

#### **Primary Objective 1 (DESCRIPTIVE).** Evaluate the intervention for feasibility

**Hypothesis 1-1.** Participant use metrics (i.e., % completion of diary, % wear-time of biosensors, frequency of video usage, % received of text messages) will be summarized with descriptive measures.

Primary Objective 2 (DESCRIPTIVE). Evaluate the intervention for acceptability (i.e., user satisfaction)

**Hypothesis 1-2.** Results of acceptability survey will be summarized with descriptive measures. Weekly interviews about app usage will be transcribed, reviewed, and analyzed by content analysis 105.

Primary Objective 3 (MACHINE LEARNING). Evaluate the mathematical robustness of the intervention by evaluating its performance to predict exercise behavior, assess exercise safety hazards, and measure exercise glycemic response.

Hypothesis 1-3-1. Predicting Exercise Behavior. The mathematical basis of the code is a binary classification model of exercise lapse using Python scikit-learn package v. 0.19.098, including random forests and gradient boosted tree ensembles (such as XgBoost99). We have completed analyses that train the model at the group level using the previous pilot dataset (section 1.2.3). These models have been pruned to reduce the complexity of the final classifiers and avoid overfitting the training data. This group-level model (Appendix 9a) will be the starting point for training a person-level model for each participant via supervised transfer learning methods during the present study to give the participant tailored prompts. This strategy mitigates the shortness of the timeframe (4 weeks) to train each person's model. At the end of the study, the data will first be used as an independent sample to validate the pilot group-level model. Second, they will be combined with the pilot data for a larger sample size to assess potential covariates, including pump vs. injection users, prior CGM usage, and age.

August 13, 2024 Version #7

If needed, separate models for subgroups can be established in the subsequent beta version of the app. Third, model-generated messages will be validated against the human-edited messages that are released to participants during the study (c.f. Sect 6.1.1, tool #2). Models are evaluated by the number of lapses required to train person-level models to reach acceptable accuracy (receiver-operator characteristic AUC .80, or precision-recall AUC .80 if <20% of days are lapses), thus estimating a "learning window" before users can expect adaptive feedback. Third,

**Hypothesis 1-3-2. Detect Exercise Safety Hazards.** Tabulate the occurrence of the common safety hazards (Table 3) and report them by frequency statistics.

**Hypothesis 1-3-3. Assessing Exercise Glycemic Response.** The mathematical basis of the R-code is our Bayesian time series model. Briefly, it compares CGM metrics over each 1-4 week period against a counterfactual predicted based upon the CGM during the 1-4 weeks before the period and the covariates over the 1-4 week period. The full formalism and an example of this analysis is available in our manuscript. The advantage over linear modeling frameworks is the flexibility to evaluate the intervention's effect strength at all points in the intervention period. If p-values do not reach significance ( $\alpha$ =.05) then the next version of the app will extend the length of the testing window before providing feedback, though even 1 week of CGM data at minimal adherence (70%) yields k=1,411 observations resulting in 96% power to detect a small effect size (d≥0.10) at  $\alpha$ =.05. The maximum window of 4 weeks was chosen as a typical minimal frequency of health coaching sessions for long-term maintenance of lifestyle change.

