# 4 Study Design

Single group completing familiarization (2 weeks), intervention (4 weeks) and follow-up (2 weeks).

The primary objectives are addressed by observation of feasibility and weekly satisfaction interviews.

The secondary objectives are addressed by longitudinal quantitative observations (surveys, wearable biosensors) during all phases and a descriptive qualitative interview at follow-up.

Figure 3. Study design flow chart.

August 13, 2024

Version #7

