# STUDY PROTOCOL Social Behavioral Template

# **6 Study Methods/Procedures**

6.1 Study Procedures

Table 1. Visit Schedule

	Pre-screening (Pre-consent)	Visit 1 Day 1	Visit 2 Day 8 ±7	Visit 3 Day 15 ±7	Visit 4 Day 22 ±7	Visits 5 Day 29 ±7	Visit 6 Day 36 ±7	Visit 7 Day 43 ±7	Visit 8 Day 50 ±7	Visit 9 Day 57 ±7	Visit 10 Day 64 ±7	Unscheduled Visit
Screening Phone Call	X											
Contact primary care provider for confirmation	X											
Informed Consent		X										
Demographics		X										
Clinical history		Χ										
Blood pressure			X	X	X	X	X	X	X	X	X	
Monitor symptoms		X	X	X	X	X	Х	X	X	X	X	
Devices			•				'				-	
InPen (if multiple daily injection user)			Continuou	ıs							>	
CGM			Continuo	ıs							>	
Fitbit			Continuo	ıs							>	
Morning survey monitoring daily living (Appendix 8a)			Continuou	ıs							>	
Actigraph GT9X (hip during day, wrist during night)			Continuou	IS	>				Continuous		>	
Intervention												
Mobile App					Continuou	s			>			
Outcome Evaluation											·	
Interview on App Features						X	X	X	X			
Exit Survey on App Features									X			

August 13, 2024 Version #7

Momentary Surveys on Motivation States									5x/day		>	
Weekly Survey on Motivation States			X	X	X	X	X	X	X	X	X	
Interview on Motivation States											X	
Adverse Events Reporting							-					
Adverse Events Reporting			X	X	X	X	X	X	X	X	X	X
Total Time (minutes)	15	30	45	35	65	65	65	65	85	35	80	15

\*The total time commitment for the study is the sum of these visits (575min) + mobile surveys (2min/survey \* 5 surveys/day \* 14 days = 140min) = 715 min, along with the target 150 minutes of exercise per week during the intervention and follow-up (150 min/week \* 6 weeks = 900min), for a total of 1625min or 27 hours.

[figure not shown]

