## VISIT 2 (Day 8)

#### **Devices**

Participants not currently using a Dexcom G6 CGM will be trained over tele-video by Research Associate [name] or PI [name]. The training protocol incorporates information from the manufacturer setup protocol plus additional guidance provided by the study endocrinologists Drs. [name] and [name] (Appendix 21). Participants will log into either their own Dexcom account (current users) or an anonymous account set up by research staff with a generic username, generic email address, and password (new users) and pair the device. They will be guided to create a "share code" that gives the holder access to CGM data in real-time; research staff will record the code on Yale's secure server for transmission to their primary diabetes care provider. The CGM is validated against venous blood glucose (mean absolute percentage error 9%-10%86,91). For the 2-week familiarization period until visit 4, the trainer will review CGM data after days 1, 3, 7, 10, and 14 days to check if data are being transmitted consistently with reasonable values and if the first sensor change (day 10) was completed as scheduled). The trainer will also talk with the participant at each weekly visit and query if there are any issues with skin irritation, sensor dislodgement, or values suspicious or inconsistent with fingerstick checks. At the visit 2 weeks after initiation (visit 4), they will ask if there were any issues with the first sensor change. Trainer will follow up with participant to troubleshoot as needed. We will start with a bank of standard troubleshooting techniques from our procedure manual, then involve Dexcom customer service or a senior clinician from the research team as needed.

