A, Based on this blood glucose data, it may be a good idea to review the recommendations from your healthcare professional about how you would adjust your food intake or insulin dosing around exercise. If you do not remember, it would be a good idea to reach out. B, If your blood sugar is high (more than 270 mg/dL) before starting exercise, check your blood or urine for ketones. If you test positive for ketones, avoid vigorous activity. If you do not have ketones in your blood or urine and you feel well, it should be fine to exercise.

Tool #4: Health outcome feedback regarding the causal impact of exercise upon blood glucose (Appendix 18). The GlucoseZone cloud will draw CGM metrics (coefficient of variation, mean, % time >180, 70-180, <70mg/dL) and covariates (insulin-on-board, carbohydrates self-reported into insulin device, exercise metrics including video selected and Fitbit minutes / heart rate / distance / calories / sleep / activity at sub-exercise intensity). The app organizes these data on a dashboard accessible to Yale staff. A Yale staff member exports the contents onto the Yale Secure Server weekly and enters them into our Bayesian R-code (Appendix 9b). The EP reviews the results and accompanying visualizations documenting a positive, neutral, or negative effect of exercise once per 1-4 weeks as insights are generated. The EP will message the client by encrypted emailed pdf relaying the most representative results and/or visualizations and any recommended adjustments by interpretating and applying exercise guidelines (e.g., "You have done purely resistance exercise for the past 28 days, and it has had the causal impact of increasing blood glucose time above target range. Consider more aerobic exercise.") If these EP's recommendations indicate repeating certain videos, they will accordingly appear on the home-screen the following week.

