The mathematical basis of the R-code is our Bayesian time series model. Briefly, it compares CGM metrics over each 1-4 week period against a counterfactual predicted based upon the CGM during the 1-4 weeks before the period and the covariates over the 1-4 week period. The full formalism and an example of this analysis is available in our manuscript¹00. The advantage over linear modeling frameworks is the flexibility to evaluate the intervention's effect strength at all points in the intervention period. If p-values do not reach significance (α=.05) then the next version of the app will extend the length of the testing window before providing feedback, though even 1 week of CGM data at minimal adherence (70%) yields k=1,411 observations resulting in 96% power to detect a small effect size (d≥0.10) at α=.05. The maximum window of 4 weeks was chosen as a typical minimal frequency of health coaching sessions for long-term maintenance of lifestyle change¹01.

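### The 96% power stated for Hypothesis 1-3-3 fits a test against a known value; against the planned estimated counterfactual a one-week window gives about 76–93%, before serial correlation and without covariate gain

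*Combined protocol and SAP*

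**What the plan says.** Section 3.2 makes it a primary hypothesis that a Bayesian model can detect exercise-related glucose changes of d≥0.1. Section 7.2 (Hypothesis 1-3-3), repeating Section 6.1.1 (Tool #4), supports this with the statement that "even 1 week of CGM data at minimal adherence (70%) yields k=1,411 observations resulting in 96% power to detect a small effect size (d≥0.10", with the significance level set to .05.

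Both sections describe the comparison. CGM metrics in each 1–4 week period are set against "a counterfactual predicted based upon the CGM during the 1-4 weeks before the period and the covariates over the 1-4 week period". Tool #4 lists several outcomes: "CGM metrics (coefficient of variation, mean, % time >180, 70-180, <70mg/dL". The exercise physiologist reviews results "documenting a positive, neutral, or negative effect of exercise once per 1-4 weeks as insights are generated". If significance is not reached, "then the next version of the app will extend the length of the testing window before providing feedback".

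The design is "Single group completing familiarization (2 weeks), intervention (4 weeks) and follow-up (2 weeks" in length. At Visit 2, "Participants will log into either their own Dexcom account (current users) or an anonymous account set up by research staff", so some participants may hold earlier readings. The plan does not say whether those would be used.

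For the 96%, the plan gives no formula, sidedness, autocorrelation, covariate R-squared or SD on which d is scaled.

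**The concern.** The power sentence uses only the number of readings in the test week. That suits a comparison with a fixed constant, but here the comparator is itself estimated from a limited run of earlier data. The sentence also counts every reading in full, although Section 6.1.1 (Tool #2) says the sensor samples every 5 minutes, and these readings come from one person.

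The 96% is the plan's only quantitative support for expecting one week of data to be enough under a primary hypothesis. If it is too high, the one-week window looks better justified than it is, and a reader may give a neutral one-week result more weight than it can bear.

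**Working it through.** **Inputs.** From Section 7.2: α=.05, d=0.10, one week at 70% capture, 1–4 prior weeks. From Section 6.1.1 (Tool #2): one reading per 5 minutes, so 12 × 24 × 7 = 2,016 per week. A two-sided test is inferred because effects in either direction are to be reported. A simple difference in means stands in for the time-series model.

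**Step 1: reproduce the plan's figure.** 0.70 × 2,016 = 1,411.2, which agrees with k=1,411. Power = Φ(d/√v − 1.96), with v the variance of the comparison in SD units. For a known comparator v = 1/1,411, so d/√v = 0.10 × √1,411 = 3.756 and power = Φ(1.796) = 96.4%. This agrees with 96%.

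**Step 2: let the comparator be estimated.** With w prior weeks and c readings captured per prior week, v = 1/1,411 + 1/(c·w). At 70% capture c = 1,411; at 90%, c = 0.9 × 2,016 = 1,814.4; at full capture, c = 2,016. Readings are still independent and covariates add nothing.

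| Prior weeks | 70% capture | 90% capture | Full capture |
|---|---|---|---|
| 1 | 75.7% | 80.4% | 82.1% |
| 2 | 86.6% | 89.0% | 89.8% |
| 3 | 90.2% | 91.7% | 92.3% |
| 4 | 91.9% | 93.0% | 93.4% |

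Example, w=2 at 70%: v = 1.5/1,411 = 0.001063, d/√v = 3.067, Φ(1.107) = 86.6%. The two familiarization weeks make w=2 the nominal case for the first app window in participants new to CGM: about 87–89%.

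**Step 3: how much serial correlation it takes.** Let F be the factor by which correlation inflates the variance of the mean. Power is 80% when d²/(F·v) = (1.960 + 0.842)² = 7.85, so F = 0.01/(7.85·v):

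- known value: 14.11/7.85 = 1.80
- 4 prior weeks at 70%: 14.11/(1.25 × 7.85) = 1.44
- 2 prior weeks at 70%: 14.11/(1.5 × 7.85) = 1.20

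Above these values power is below 80%. This needs no correlation model.

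**Illustration only, mean glucose only.** Under an assumed AR(1), F = (1+ρ)/(1−ρ) if the missing 30% falls in one block, and F = 1 + 2(0.7)ρ/(1−ρ) if it is scattered. The 80% limit is then crossed at ρ of about .09–.12 (2 prior weeks), .18–.24 (4 prior weeks) or .29–.36 (known value). At ρ=.5, F is 3.0 or 2.4, and power with 2 prior weeks is 43–51%. The documents give no ρ.

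**Step 4: what covariates would have to do.** With independent readings, 70% capture and d in raw-SD units, restoring 96.4% needs R² = 1 − 1/(1+1/w): 1 − 1/1.5 = .33 for 2 prior weeks and 1 − 1/1.25 = .20 for 4. No R² is stated.

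**The case against.** The plan's arithmetic is not wrong: 1,411 and 96% both reproduce. The dispute is over assumptions that the sentence leaves unstated. That is a fair description, but the assumption of a known comparator conflicts with the comparison described in the same paragraph.

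A reader might infer that 96% can arise only from a known comparator. That is too strong. A one-sided test with 4 prior weeks gives 95.7% at 70% capture, and one-sided tests with 3 or 4 prior weeks at 90% capture give 95.6% and 96.3%. A two-week window against two prior weeks, two-sided, also gives 96.4%, because ½ + ½ = 1 in the variance. All still assume independence. The one-sided versions do not fit reporting effects in both directions, and the last is not a one-week window.

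The 70% capture in the prior weeks is a choice. Section 7.1 expects 90% CGM wear, and Section 1.2.1 reports 92.5% at the pilot baseline. This objection stands, so both rates are shown; even full capture with 4 prior weeks reaches only 93%.

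A reader might also take the ±7-day visit windows in Table 1 to mean that prior data could run from 0 to 28 days. The Visit 2 text does not support this: it places Visit 4 two weeks after CGM initiation and schedules data checks through day 14.

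The design effects in Section 7.1 are not a direct precedent either. They concern clustering of survey responses across people, not serial correlation within one person.

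Finally, the planned time-series model may handle correlation well. That would make the analysis sound, but it would not validate a power figure computed from the raw count.

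**Conclusion.** The 96% does not describe the planned one-week comparison. Against a counterfactual estimated from 1–4 prior weeks, power is 76–92% at 70% prior-week capture or 80–93% at 90%, and nominally about 87–89% for the first app window in participants new to CGM. These figures assume a two-sided test, independent readings, no covariate gain and a difference in means as proxy for the model. Serial correlation lowers them and covariates may raise them; the documents allow neither effect to be sized. It would be tempting to conclude that true power is very low, but that rests on an assumed ρ, and the AR(1) figures do not cover the coefficient of variation or the time-in-range metrics.

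The consequence is limited. The sample size of 24 rests on other grounds (Section 7.1), and the 4-week maximum has its own rationale. A reader might infer that the plan would treat a non-significant week as evidence of no effect. Its only written response is to lengthen the window in the next app version, which treats the result as too little data. What remains is an overstated justification for a one-week window under a primary hypothesis, which should be corrected.

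**What to change.** Delete the 96% power clause in Section 6.1.1 (Tool #4) and Section 7.2 (Hypothesis 1-3-3).

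Alternatively, replace it with power and detectable d obtained by simulating the planned time-series model on the pilot CGM series (Section 1.2.1). Limit this to the window lengths and prior weeks that those series support: the pilot section reports capture only for baseline and weeks 9–10, so longer continuous runs should not be presumed. State the sidedness, the prior-week capture and the SD on which d is based, and say whether readings from participants' own CGM accounts count as prior weeks.

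Deletion costs wording in two places. Replacement adds one simulation on pilot data. Enrolment and data collection do not change. The downside is a less favourable stated power.

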#### 7.2.1 Secondary Objective Analyses (if applicable)

All statistical models for secondary objectives 1 and 2 will estimate intraclass correlation coefficient (ICC) to assess the proportion of variance explained by participant ID.

Secondary Objective 1 (STATISTICAL, MULTILEVEL MODELING). Examine whether recognized T1D-related physical activity barriers (fear of hypoglycemia, glycemic variation) predict momentary and long-term variation in motivation states for physical activity

**Hypothesis 2-1-1. Momentary predictors of motivation states.** We will develop two multilevel models for the dependent variables of want and aversion for physical activity (CRAVE 2-item "right now") respectively. The independent variables and covariates (Table 2) will be separated into momentary states for level 1, daily states for level 2, and demographics for level 3.

Hypothesis 2-1-2. Week-to-week changes in motivation states. We will develop two generalized linear mixed models for the dependent variables of want and aversion for physical activity (CRAVE 10-item "right now") respectively. A random intercept will incorporate correlations within-subject. We will include long-term assessed independent variables and covariates (Table 2, last column) along with a time categorical variable to estimate the contribution of changes coinciding with intervention (T0 to T1) and maintenance follow-up (T1 to T2).

Secondary Objective 2 (STATISTICAL, MULTILEVEL MODELING). Examine whether motivation states for physical activity predict momentary and long-term variation in physical activity behavior change, adherence, and maintenance resulting from a T1D motivational physical activity intervention.

August 13, 2024

Version #7

Hypothesis 2-2-1 – Predictors of physical activity behavior change and adherence over the intervention. We will develop a generalized linear mixed model for physical activity behavior testing WANT and SCT constructs as independent variables. A random intercept will incorporate correlation within-subject. We will include long-term assessed independent variables and covariates (Table 2, last column) along with a time categorical variable to estimate the contribution of changes from intervention (T0-T1) and maintenance follow-up (T1-T2).

**Hypothesis 2-2-2 – Predictors of acute physical activity behavior.** We will develop a multilevel logistic model where the dependent variable is a binary physical activity behavior outcome, defined as absence vs. presence within 3hr window of 10+ min bout of moderate-to-vigorous physical activity with no more than 2min interruption. The models will include the same levels as hypothesis 2-1-1. We will estimate unadjusted and adjusted odds ratios of physical activity behaviors.

Secondary Objective 3 (QUALITATIVE). Qualitatively identify determinants and sequalae of motivation states for physical activity.

**Hypothesis 2-3.** De-identified transcripts will be imported into NVivo by [name] from Case-Western Reserve University or designee. Drs. [name] and [name] will collaboratively identify general coding categories. [name], a research assistant (RA) from Case-Western Reserve University, and [name] will meet to establish consensus on the coding. Drs. [name] and [name] will identify subthemes and the RA will conduct the remaining coding of excerpts into subthemes in NVivo. This process is recommended for descriptive studies as it involves immersion in the data prior to specific coding, emphasizing theorizing, synthesizing, and recontextualizing. We will incorporate field notes with interviewer impressions and observations. We will use inductive, directed qualitative content analysis. Emerging findings will inform continual refinement of questions and probes. Results will be reviewed with mentor [name] every 2 weeks.

